8.2.7. Markers of Hemolysis

Blood samples for the following markers of hemolysis will be collected pre-dose on Days 0 and 3:

- direct Coomb's test (DCT)
- serum lactate dehydrogenase (LDH)
- plasma free hemoglobin
- serum haptoglobin
- serum bilirubin

A urine sample for urine hemosiderin will be collected at the same timepoints.

If the DCT result at Day 3 is positive or not available by Day 5, blood and urine samples will be collected pre-dose on Day 5 for testing of all the above markers, as well as an unscheduled CBC. If any result at Day 5 is suggestive of hemolysis (*i.e.*, positive DCT; plasma free hemoglobin, LDH, serum bilirubin, or urine hemosiderin above the normal reference range; haptoglobin below the normal reference range) all markers including CBC will be tested pre-dose at Day 7. Similarly, if any result at Day 7 is suggestive of hemolysis; all markers including CBC will be tested pre-dose at Day 14.

Markers of hemolysis will be reviewed regularly by the medical monitor, and any potential signs of hemolysis will be reported to the investigator, sponsor and dedicated CRO by the central laboratory within one business day.

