10.6.4. Hematology, Serum Biochemistry, Urinalysis

Hematology, serum biochemistry and urinalysis variables will be summarized, including changes from baseline.

Shift tables for hematology and biochemistry variables will be provided for the number and percentage of subjects with values below, within and above the reference range.

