2.3 Clinical Laboratory and Other Adverse Events

If a laboratory result is considered by the investigator to be clinically significant or have a clinically significant pathological change from baseline it should be recorded as an AE.

Other abnormal results (e.g. x-rays, scans, physical examination findings) that worsen from baseline and/or are considered clinically significant should also be recorded as AEs.

The investigator will exercise his or her medical and scientific judgment in deciding whether an abnormal laboratory finding or other abnormal assessment is clinically significant.

AEs should be reported and documented in accordance with the procedures outlined below. All AEs occurring during the study must be documented on the relevant CRF/e-CRF pages. The following data should be documented for each AE:

- Description of the symptom event
- Classification of 'serious' or 'not serious'
- Severity
- Date of first occurrence and date of resolution (if applicable)
- Action taken
- Causal relationship
- Outcome of event (unknown, recovered, not recovered, recovered with sequelae, death [with date and cause reported])

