Hematology *	Mild (Grade 1)	Moderate (Grade 2)	Severe (Grade 3)	Potentially Life Threatening (Grade 4)
Hemoglobin (Female) - gm/dL	11.0 – 12.0	9.5 – 10.9	8.0 – 9.4	< 8.0
Hemoglobin (Female) change from baseline value - gm/dL	Any decrease – 1.5	1.6 – 2.0	2.1 – 5.0	> 5.0
Hemoglobin (Male) - gm/dL	12.5 – 13.5	10.5 – 12.4	8.5 – 10.4	< 8.5
Hemoglobin (Male) change from baseline value – gm/dL	Any decrease – 1.5	1.6 – 2.0	2.1 – 5.0	> 5.0
WBC Increase - cell/mm ³	10,800 – 15,000	15,001 – 20,000	20,001 – 25,000	> 25,000
WBC Decrease - cell/mm ³	2,500 – 3,500	1,500 – 2,499	1,000 – 1,499	< 1,000
Lymphocytes Decrease - cell/mm ³	750 – 1,000	500 – 749	250 – 499	< 250
Neutrophils Decrease - cell/mm ³	1,500 – 2,000	1,000 – 1,499	500 – 999	< 500
Eosinophils - cell/mm ³	650 – 1500	1501 - 5000	> 5000	Hypereosinophilic
Platelets Decreased - cell/mm ³	125,000 – 140,000	100,000 – 124,000	25,000 – 99,000	< 25,000
PT – increase by factor (prothrombin time)	1.0 – 1.10 x ULN**	1.11 – 1.20 x ULN	1.21 – 1.25 x ULN	> 1.25 ULN
PTT – increase by factor (partial thromboplastin time)	1.0 – 1.2 x ULN	1.21 – 1.4 x ULN	1.41 – 1.5 x ULN	> 1.5 x ULN
Fibrinogen increase - mg/dL	400 – 500	501 – 600	> 600	--
Fibrinogen decrease - mg/dL	150 – 200	125 – 149	100 – 124	< 100 or associated with gross bleeding or disseminated intravascular coagulation (DIC)

* The laboratory values provided in the tables serve as guidelines and are dependent upon institutional normal parameters. Institutional normal reference ranges should be provided to demonstrate that they are appropriate.

** "ULN" is the upper limit of the normal range.

Urine *	Mild (Grade 1)	Moderate (Grade 2)	Severe (Grade 3)	Potentially Life Threatening (Grade 4)
Protein	Trace	1+	2+	Hospitalization or dialysis
Glucose	Trace	1+	2+	Hospitalization for hyperglycemia
Blood (microscopic) – red blood cells per high power field (rbc/hpf)	1 - 10	11 – 50	> 50 and/or gross blood	Hospitalization or packed red blood cells (PRBC) transfusion

* The laboratory values provided in the tables serve as guidelines and are dependent upon institutional normal parameters. Institutional normal reference ranges should be provided to demonstrate that they are appropriate.

Contains Nonbinding Recommendations

IV. REFERENCES

1. National Cancer Institute Common Toxicity Criteria, April 30, 1999. (<http://ctep.cancer.gov/reporting/CTC-3.html>)

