Specifically, the following two analyses will be performed to assess impact on primary PK analysis:

- The primary PK analysis will be repeated assuming that non-compliant subjects did not attain an RVNA titer of ≥ 0.5 IU/mL at Visit 6. [worst case scenario]
- The primary PK analysis will be repeated assuming that non-compliant subjects successfully attain an RVNA titer of ≥ 0.5 IU/mL at Visit 6. [best case scenario]

j. SUBGROUP ANALYSES

Subgroup analyses will be performed as appropriate, due to either imbalance randomization in baseline subject demographics and/or clinical relevance to primary and secondary PK analyses and safety analysis. Factors including, but not limited to, age, race, BMI, and sex will be considered. Subgroups will be defined based on population median.

K. MISSING VALUES

No missing value imputation methods will be applied, e.g. the analyses are based on a valid case basis.

I. INJECTION SITE OBSERVATIONS

Injection site observations data will be summarized as appropriate.

SUMMARY BY PRODUCT

The number and percentage of subjects reporting injection site reactions will be summarized by preferred term and product (HRIG or vaccine).

SUMMARY BY NUMBER OF INJECTIONS

The number and percentage of subjects reporting injection site reactions will be summarized by preferred term, product (HRIG or vaccine) and number of injections.

M. VIRAL SEROLOGY VARIABLES

Viral serology variables will be summarized. Shift tables for virology will present the number of subjects with positive and negative results and those for whom the results change during the study.

N. HEMATOLOGY, SERUM BIOCHEMISTRY, URINALYSIS

Hematology, serum biochemistry and urinalysis variables will be summarized, including changes from baseline. Shift tables for hematology and biochemistry variables will be provided for the number and percentage of subjects with values below, within and above the reference range.

O. MARKERS OF HEMOLYSIS

Markers of hemolysis will be summarized, including changes from baseline.

p. VITAL SIGNS AND BODY TEMPERATURE

Sitting diastolic and systolic blood pressure, pulse rate, body temperature and respiration rate will be summarized, including changes from baseline (i.e. pre-dose on Visit 2 for body temperature, Screening for all other parameters). In addition, the number of subjects with “substantial” increases or decreases from baseline in blood pressure (>20 mmHg) and pulse (>15 b.p.m.) will be summarized.

q. PHYSICAL EXAMINATION

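### Laboratory changes are not counted by toxicity grade per arm, so a Grade 3 hemoglobin fall within the reference range is counted only if the investigator reports it as an adverse event

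*Protocol*

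**What the plan says.** Protocol 10.6.4 and SAP 8.N plan the same two outputs. The first is descriptive: "Hematology, serum biochemistry and urinalysis variables will be summarized, including changes from baseline". The second, for hematology and biochemistry only, is a shift table giving the "number and percentage of subjects with values below, within and above the reference range". Urinalysis has no shift table.

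Appendix A, Section 7 of the protocol reproduces a toxicity grading guidance. The hematology table in its Part B has rows "Hemoglobin (Female) change from baseline value - gm/dL" and "Hemoglobin (Male) change from baseline value – gm/dL". In both, a fall of 1.6-2.0 g/dL is Grade 2, 2.1-5.0 is Grade 3 and more than 5.0 is Grade 4. The protocol cites this guidance for grading injection-site reactions (8.2.2) and as further information on adverse event (AE) severity (Appendix A, 3.4). Neither document says that every laboratory value will be graded.

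A laboratory finding reaches the AE tables through Appendix A, 2.3: a result that is "clinically significant or have a clinically significant pathological change from baseline it should be recorded as an AE". The investigator's judgment is decisive "in deciding whether an abnormal laboratory finding or other abnormal assessment is clinically significant".

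Routine hematology is taken at Screening and Day 140 (8.2.5). Under 8.2.7, a Day 3 direct Coombs test that is positive, or not available by Day 5, triggers a Day 5 repeat of the hemolysis markers "as well as an unscheduled CBC". Further testing on Days 7 and 14 depends on the preceding result.

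**The concern.** Objective 4 is a safety comparison between the two products, and Protocol 10.6 says the summaries will be examined for clinically relevant imbalance. A three-level shift is a coarse tool for that. A large fall from a high-normal start appears as within-to-within, that is, as no shift. Values just below the limit and far below it share one cell.

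The plan already counts subjects whose blood pressure changes by more than 20 mmHg or whose pulse changes by more than 15 bpm (10.6.6). Laboratory values have no equivalent count, although the protocol watches hemolysis with its own marker panel and triggered repeat testing. An imbalance in moderate or severe laboratory changes that investigators did not report as AEs could be missed in the by-arm tables.

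**Working it through.** The plan states no figure on this point, so there is none to reproduce. The check sets the scale's cut-offs against the planned tables.

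**Inputs**
- Grade 3 fall: 2.1-5.0 g/dL, both sexes (Appendix A, Section 7.B).
- Upper bound of Grade 1 on the absolute rows: 12.0 g/dL (female), 13.5 g/dL (male) (same table).
- Platelets: 125,000-140,000 is Grade 1; below 25,000 is Grade 4 (same table).
- Subjects per arm: 81 (Protocol 4.1).
- Assumption: the documents give no laboratory reference ranges, so the Grade 1 upper bounds stand in for the lower reference limits.
- Assumption: a fall of 3.0 g/dL per affected subject, to illustrate the effect on the mean.

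**Step 1. Can a Grade 3 fall stay in range?** Required start = lower limit + 2.1.
- Women: 12.0 + 2.1 = 14.1, so any start above 14.1 g/dL.
- Men: 13.5 + 2.1 = 15.6, so any start above 15.6 g/dL.
- Example: a man going from 16.5 to 14.0 falls by 2.5 g/dL. That is Grade 3 on the change row and ungraded on the absolute row. It shows as no shift if both values lie in the laboratory's range.

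**Step 2. Does the shift separate severities out of range?** A platelet count of 130,000 is Grade 1 and one of 20,000 is Grade 4. If the laboratory's lower limit is above 130,000, both fall in the same cell.

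**Step 3. Would the mean change reveal it?** Shift in arm mean = k x 3.0 / 81 for k affected subjects.
- k = 1: 3.0/81 = 0.04 g/dL (1.2% of the arm)
- k = 3: 9.0/81 = 0.11 g/dL (3.7%)
- k = 5: 15.0/81 = 0.19 g/dL (6.2%)

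A count would show 1, 3 or 5 subjects directly. The minimum change shows only the single largest fall in each arm.

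**Step 4. How reliable is the AE route for these cases?**
- Protocol 7.10 has the investigator review every report, but asks for an assessment of clinical significance only for values outside the normal range. An in-range fall does not trigger that step.
- Appendix A, 3.4 grades AEs by interference with activity and need for medical intervention. A symptom-free Grade 3 fall that is reported could be graded mild.
- The AE severity tables (Protocol 10.6.1, SAP 8.h) order only severe, moderate and mild; Grade 4 is not named.

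**Step 5. Where do triggered blood counts go?** They are additional to the marker list in 8.2.7. Neither the hematology section nor the hemolysis section of the analysis plan says how unscheduled values are tabulated.

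**Step 6. Urinalysis.** The scale grades urine protein and glucose as trace, 1+ and 2+. Results of that kind have no numeric change from baseline, yet that is the only baseline comparison the plan names for them.

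**The case against.** The strongest reply is that the plan already has a route for important changes. Clinically significant results and changes must be recorded as AEs, and AEs are tabulated by arm and maximum severity. A reader might infer that graded changes are never counted by arm. The documents do not support that. What goes uncounted is a graded change that the investigator does not judge clinically significant, and a platelet count of 20,000 would very plausibly be reported.

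A reader might also infer that the protocol adopted the scale for laboratory data and then failed to use it. That does not stand either. The scale is appended nonbinding guidance, describes grading as supplementary to full data analysis, and is cited only for injection-site and AE severity. Its footnotes recommend that reference ranges be provided; they do not require it.

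Nor do the documents exclude triggered blood counts from the shift table. They are silent.

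Three further points have force:
- Protocol 10.3 and SAP 7 plan minimum and maximum, and Protocol 10.3 has all data listed, so extreme values would be visible. SAP 8.a omits minimum and maximum but allows other statistics. Extremes and listings still do not count subjects by arm.
- Early hemolysis is assessed in all subjects by the marker panel on Days 0 and 3, summarized separately (Protocol 10.6.5, SAP 8.O). Without a triggered count, a subject's only post-baseline hemoglobin is at Day 140, 20 weeks after the single HRIG dose. This limits what a hemoglobin grade table can say about hemolysis.
- Categorical data get counts and percentages by general convention, so dipstick categories would be tabulated. The gap is the missing category shift.

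**Conclusion.** The point holds as a worthwhile, inexpensive improvement to the safety tables. It is not a broken commitment, and it affects no efficacy conclusion. No planned table counts laboratory changes by grade per arm. A Grade 3 hemoglobin fall within the reference range is counted only if the investigator reports it, and the three-level shift cannot separate mild from severe values outside the range.

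The thresholds of 14.1 and 15.6 g/dL rest on the assumed reference limits and move one-for-one with the central laboratory's actual ones. The effect on the mean scales with the assumed 3.0 g/dL fall. How many such falls will occur cannot be estimated from the documents, and the sparse hematology schedule suggests a modest yield.

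**What to change.** In Protocol 10.6.4 and SAP 8.N, add a supplementary descriptive table by arm:

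- Number and percentage of subjects by worst post-baseline Section 7.B grade, restricted to Grade 2 or above and increased from baseline. Starting at Grade 2 avoids noise from the hemoglobin change row, where any decrease up to 1.5 g/dL is Grade 1.
- Include the hemoglobin change-from-baseline rows for both sexes, with Screening, the only scheduled pre-dose hematology, as baseline.
- State that all unscheduled and triggered blood counts from Days 5, 7 and 14 enter the worst-grade derivation.
- Check the cut-offs against the central laboratory's reference ranges before unblinding and record any adjustment.
- For dipstick urinalysis, replace change from baseline with a category shift table.

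Keep the existing summaries and shift tables for hematology and biochemistry. All data are already collected, so the cost is SAP wording and programming time for one or two tables. The limitation to state with the table is that most subjects will contribute only a Screening and a Day 140 hematology value.

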APPENDIX B. - ADMINISTRATIVE REQUIREMENTS

1. ABBREVIATIONS AND DEFINITIONS

ARSAC	- Administration of Radioactive Substances Committee
BPL	- Bio Products Laboratory Limited
CA	- Competent Authority
COI	- Coordinating Investigator
CI	- Chief Investigator
CRA	- Clinical Research Associate
CRF	- Case Record Form
e-CRF	- Electronic Case Record Form
CV	- Curriculum Vitae
DQF	- Data Query Form
EU	- European Union
FDA	- Food and Drug Administration
GCP	- Good Clinical Practice
GMC	- General Medical Council
HIV	- Human Immunodeficiency Virus
ICH	- International Conference on Harmonisation
ID	- Identification
IEC	- Independent Ethics Committee
IMP	- Investigational Medicinal Product
IRB	- Institutional Review Board
PI	- Principal Investigator
R&D	- Research and Development
SOP	- Standard Operating Procedure

CA – ‘Competent Authority’, synonymous with ‘Regulatory Authority’: the Government body that has the power to regulate. In the context of ICH GCP, the term ‘Competent Authority’ includes the authorities that review submitted clinical data and those that conduct inspections.

CI – ‘Chief Investigator’: in relation to a clinical trial conducted at a single trial site, the Investigator for that site. In relation to a clinical trial conducted at more than one trial site, the authorised health care professional, whether or not he/she is an Investigator at any site, who takes primary responsibility for the conduct of the trial.

COI – ‘Coordinating Investigator’: an investigator assigned the responsibility for the coordination of investigators at different centres participating in a multicentre trial.

PI - ‘Principal Investigator’: a doctor or person following a profession for investigations because of the scientific background and the experience in subject care it requires. The Principal Investigator is responsible for the conduct of the trial at the trial site. If a trial is conducted by a team of individuals at a trial site, the Principal Investigator is the leader responsible for the team.

IEC – ‘Independent Ethics Committee’: a review board or a committee, institutional, regional, national or supranational, constituted of medical/scientific professionals and non-medical/non-scientific members, whose responsibility it is to ensure the protection of the rights, safety and well-being of human subjects involved in a clinical trial and to provide public assurance of that protection, by, among other things, reviewing and approving / providing favourable opinion on, the trial protocol, the suitability of the Investigator(s), facilities and the methods and material to be used in obtaining and documenting informed consent of the trial subjects.

IRB – ‘Institutional Review Board’: an independent body constituted of medical, scientific and non-scientific members, whose responsibility is to ensure the protection of the rights, safety and well-being of human subjects involved in a clinical trial by, among other things, reviewing, approving and providing continuing review of the trial protocol and amendments and of the methods and material to be used in obtaining and documenting informed consent of the trial subjects.

IMP – ‘Investigational Medicinal Product’: a pharmaceutical form of an active substance or placebo being tested or used as a reference in a clinical trial, including products already with a marketing authorisation but used or assembled in a way different from the authorised form, or when used for an unauthorised indication, or when used to gain further information about the authorised form.

2. ETHICAL CONSIDERATIONS

The study will be performed in accordance with the guidelines of the Declaration of Helsinki on biomedical research involving human subjects and in accordance with GCP guidelines (ICH), EU Directives 2001/20/EC¹ and 2005/28/EC² and FDA’s Code of Federal Regulations (CFR)³ 21 CFR parts 50, 54, 56, 312 and 314 as well as the demands of national drug and data protection laws, other applicable regulatory requirements and any new directives or regulations which become enforceable during the course of the study.

Before the study can begin the Investigator must have submitted to an Independent Ethics Committee (IEC) / Institutional Review Board (IRB) the study protocol, Investigator’s Brochure, subject

information leaflet, consent form (and any updates), subject recruitment procedures and any other relevant study documentation as outlined in the guidance document ('Detailed guidance on the application format and documentation to be submitted in an application for an Ethics Committee opinion on the clinical trial on medicinal products for human use', ENTR/CT 2) for EU Directive 2001/20/EC¹. Written approval of the study must be obtained before the study centre can be initiated or the investigational medicinal product (IMP) can be released to the Investigator. Any necessary extensions or renewals of IEC / IRB approval must be obtained for changes to the study such as modification of the protocol, the informed consent form, the written information provided to subjects and/or other procedures.

The Investigator will report promptly to the IEC / IRB any new information that may adversely affect the safety of the subjects or the conduct of the study. The Investigator will submit written summaries of the study status to the IEC / IRB annually, or more frequently if requested by the IEC / IRB, in accordance with local regulatory requirements. On completion of the study, the sponsor will notify the IEC / IRB that the study has ended.

3. INFORMED CONSENT

No study-related procedures will be performed prior to the subject's and subject's parent/legal guardian's (if applicable) signed consent to participate in the study being obtained. Before the decision to participate, the Investigator or a duly authorised deputy will provide both an oral and a written full explanation of the study and the subject's rights. The written consent must be given by the subject and the parent/legal guardian (if applicable) of the subject, after detailed information about the study has been given as outlined above in EU Directive 2001/20/EC¹ and in accordance with any national provisions on the protection of clinical study subjects. The verbal explanation will cover all the elements specified in the written information provided for the subject.

For subjects not qualified to give legal consent, written consent must be obtained from the subject's parent/legal guardian. If appropriate, children old enough to understand the risks and benefits of the study (generally for children above 6 years of age) should also be informed and provide their written assent. In addition, the subject/subject's parent or legal guardian will sign consent and child's assent form authorizing release of the subject's HIV test results to appropriate authorities. All consent and assent forms must be approved in advance by the IRB/IEC.

If the legal guardian is unable to read, an impartial witness should be present during the entire informed consent discussion. After the informed consent form and any other written information is provided, read, and explained to the subject or their legal guardian, and after oral consent has been obtained, if

capable of doing so, the subject's legal guardian should sign and date the informed consent form, and where appropriate written assent should be obtained from the subject. The witness should also sign and date the consent form. In addition, the subject's legal guardian should, if possible, sign an additional form confirming that the materials provided have been read and explained to them. The witness should also sign and date this additional form.

The Investigator or designated personnel will inform the subject of the objectives, methods, anticipated benefits and potential risks and inconveniences of the study. The subject and parent/legal guardian (if applicable) must be given every opportunity to clarify any points they do not understand and, if necessary, to ask for more information. At the end of the interview, the subject and parent/legal guardian (if applicable) will be given time to consider the study if this is required, or if they request more time. Subjects and parents/legal guardians (if applicable) will be required to sign and date the informed consent form. After signatures are obtained, the informed consent forms will be kept and archived by the Investigator in the Investigator's study file for possible inspection by regulatory authorities, the IEC or IRB, BPL or BPL's representative's personnel, auditors. The subject will keep an identical signed copy. A letter will be sent to the subject's primary care physician informing him/her that the subject is to participate in the study, as appropriate.

It should be emphasised to the subject that he/she is at liberty to withdraw from the study at any time, without penalty or loss of benefits to which the subject is otherwise entitled. Subjects who withdraw consent should not continue in the study, but will be asked to attend an end-of-study visit, if possible.

The IEC / IRB will review and approve the subject information sheet and informed consent form. If the Investigator intends to use his/her own information leaflet (for non-interventional studies only) he/she must ensure that it contains all the information outlined in Section 4.8 of the ICH-GCP guidelines.

